5.1 Rehabilitation for Total Knee Replacement

Physical therapy (PT) is an important component of care for patients who have total knee replacement (TKR) surgery. The focus of this rehabilitative care is to promote mobilization and the achievement of functional goals. A meta-analysis evaluating the effectiveness of post-surgical PT in 18 randomized clinical trials for a total of 1,739 patients with primary TKR concluded that patients who received PT had improved physical function and decreased pain at 3-4 months after hospital discharge, and the benefit extended to 6 months in some studies.¹ In the United States, PT after hospital discharge is provided in rehabilitation facilities, in the home by home health therapists, and in community-based clinics. Although widely supported as the standard of care with evidence of effectiveness, there is significant variation in what is provided, to whom, and for what duration. Post-acute care including utilization of PT for joint replacement is the single largest driver in the variation of Medicare spending.²

Gaps exist in the ability of PT to support all patients in need, including a projected nationwide shortage of therapists, few therapists available in underserved areas, and limited numbers of PT visits covered by insurance for those who have it. These gaps make it necessary to develop other effective, low-cost and accessible options to help patients regain physical function after TKR, and improve pain and other patient-centered outcomes.

5.2 Study Purpose

This randomized clinical trial will compare the costs and clinical effectiveness of traditional PT versus a technology-supported home-based PT rehabilitation program for patients with TKR. The primary aim of this project is to determine if a technology-supported home-based PT rehabilitation program is a cost-saving approach and at least clinically equivalent to traditional PT.

5.3 Study Rationale

The use of digital technology where the patient and therapist can interact both in real-time and asynchronously (e.g., patient completes recommended activities and therapist reviews performance at different times) can alleviate scheduling issues for both the therapists and patients, allowing therapists to potentially manage more patients (higher case load) and patients to follow recommendations and complete activities when most convenient. Having the PT program entirely available to the patient via technology may be cost efficient for both the patient and health system as more therapy sessions could be completed by the patient on their own schedule, without co-pays, and requiring less real-time PT supervision over time.

6 OVERVIEW

6.1 Synopsis

This is a multi-center, randomized, clinical trial to evaluate the costs and clinical effectiveness of technology-supported home-based physical therapy (PT) compared with traditional PT in the home or clinic. Duke University and Duke Clinical Research Institute (DCRI), along with the sponsor, Reflexion Health, Inc., will be responsible for the design, implementation, and leadership of the VERITAS study. Data analysis and publications will be managed according to a written plan designed to maintain appropriate scientific oversight and rigor by the DCRI. A Data Monitoring Committee (DMC) will not be used.

This trial will include subjects scheduled for a total knee replacement (TKR), as defined by protocol inclusion and exclusion criteria. All subjects will receive standard of care as defined by current site-specific and local guidelines for the management of TKR.

A total of 300 randomized subjects are planned for this study. Subjects will be randomized in a 1:1 ratio, stratified by site, to receive either tele-rehab-supported PT or traditional home and/or clinic-based PT.

6.2 Study Objectives

6.2.1 Primary Objective:

The primary objective is to compare the effects of tele-rehab-supported PT versus traditional home and/or clinic-based PT for TKR on health service use costs at 12-weeks postoperative.

Hypothesis (Superiority Test): Patients who receive tele-rehab-supported PT will have lower total episode of care costs compared with patients in the traditional PT group at 12-weeks.

6.2.2 Secondary Objective:

The secondary objectives are to compare tele-rehab-supported PT and traditional PT on patient-centered outcomes as follows:

- a. Effectiveness hypothesis (Non-Inferiority Test): The tele-rehab intervention will be non-inferior to traditional PT at 6 weeks (differences between groups <5% for clinical and patient-reported outcomes) and 12 weeks (difference <5% patient-reported outcomes).
- b. Safety hypothesis (Non-Inferiority Test): The tele-rehab intervention will be non-inferior to traditional PT at 12 weeks (pain, falls, and self-reported number of re-hospitalizations).

6.2.3 Exploratory Objectives:

The final objectives (exploratory analyses) are to determine if superiority between PT methods exist for the endpoints primarily tested for non-inferiority, determine whether individual patient characteristics are associated with differential improvement from 6 to 12 weeks assessed by patient-reported outcomes, and to determine the cost for the VERA system such that the cost between the control group and intervention groups is cost-neutral, assuming that the intervention group is determined to cost less.

7 Study Design

7.1 Overview

VERITAS (Virtual Exercise Rehabilitation In-home Therapy: A Randomized Study) is a multi-center randomized clinical trial aimed at evaluating both the costs and clinical effectiveness of technology-supported home-based physical therapy (PT) compared with traditional PT in the home or clinic. Patients in both groups will be prescribed exercises by a physical therapist. The trial is focused on the delivery of the PT program: VERA™ in the home with virtual PT support compared to PT provided through traditional methods (e.g., home health, clinic, or printed instructions). This study will recruit patients at approximately 6 surgical practice groups (either one site or group of local sites) to enroll 300 patients with unilateral total knee replacement (TKR) who are planned to return home after hospital discharge.

Once authorized to begin, sites will pre-screen patients scheduled for TKR for eligibility. The baseline study visit will be completed at least 10 days prior to surgery. After informed consent is obtained, patients will complete the baseline assessments and be randomized to either tele-rehab supported PT (Vera™) or traditional PT. Intervention group patients will have the tele-rehab system installed in their home prior to surgery, virtually meet the physical therapist, receive recommendations for a pre-operative exercise program ("prehab"), and continue the recommended tele-rehab PT program after hospital discharge until discharged by the physical therapist. Control group patients will follow the clinical team's recommendations for PT as organized and delivered in traditional care (home health, clinic, paper instructions). There are no differences in risk to patients between the two study arms.

Data will be collected at the following time points, and is detailed in Table 1 below:

- Pre-enrollment: Screening log (monthly submission)
- Baseline (≥ 10 days prior to surgery): Randomization CRF, patient contact information and medical record release, patient surveys, and baseline case report form (CRF)
- Hospital discharge: CRF
- 6 weeks after surgery: CRF, patient surveys, and patient diary (collected by DCRI Call Center)
- 12 weeks after surgery: Patient surveys and patient diary (collected by DCRI call center), as well as chart review for service utilization (among select sites)

Table 1: Schedule of Assessments

Activity	Screening	Enrollment / Baseline	D/C	6 weeks post-op	12 weeks post-op
Complete screening log for all patients	X ¹				
Invite patient to participate via letter or other IRB-approved method	X ²	X ²			
RAPT score and living situation assessment	X ²	X ²			
Consent and randomization		X ³			
Medical record release, patient contact form		X			
Gait speed measurement		X ⁴	X ⁴	X ⁴	
Range of motion measurement				X ⁴	
Data collection form entered in DCRI Registry System		X	X	X	
Chart review for health resource use					X
Patient-reported health outcomes*					
KOOS		X ⁵		Call Ctr	Call Ctr
PROMIS Global Health		X ⁵		Call Ctr	Call Ctr
Satisfaction with Physical Function		X ⁵		Call Ctr	Call Ctr
Adherence to PT regimen				Call Ctr	Call Ctr
Pain ⁶			X ^{4,6}	Call Ctr ⁶	Call Ctr ⁶
Falls		X ⁶ (in prior 3m)	X ⁴	Call Ctr	Call Ctr
Physical activity		X ⁶		Call Ctr	Call Ctr
Healthcare encounters / service use		X ⁶ (hosp. in prior 3m)		Call Ctr (pt diary)	Call Ctr (pt diary)
Thoughts about tele-rehab system ⁷					Call Ctr

* Two additional outcomes were incorporated into the 6 and 12 week interviews, addressed in elsewhere in the protocol: return to work and personal recovery goal.

¹ Submitted monthly via email to DCRI Coordinating Center.

² Completed at either time point as approved by local IRB.

³ If surgery date is unknown at time of consent, randomization may be delayed, but must occur no less than 10 days prior to surgery.

⁴ Results recorded in medical record and entered on data collection form in DCRI Registry System.

⁵ Baseline assessments collected by study site and faxed to DCRI Call Center.

⁶ Collected using pain scale from PROMIS survey when full PROMIS is not administered.

⁷ Collected only among patients randomized to tele-rehab.

7.2 Study Effectiveness and Safety Endpoints

7.2.1 Primary Effectiveness Endpoint

The total health service use costs at 12-weeks postoperative will be compared between patients who receive tele-rehab-supported PT versus traditional home and/or clinic-based PT for TKR.

For this analysis, the cost for each group will be determined by assigning pre-determined costs for activities collected in the patient's diary. A diary form will be given to each patient after randomization, as a method to support recall of healthcare interactions during the 6- and 12-week follow-up interviews. Patients will be instructed to use the diary to collect any interactions with the healthcare system that occur after they are discharged from the

hospital following their surgery. Encounters of interest will include in-person PT visits, doctor visits, phone calls or emails to a PT or doctor, visits to an urgent care center or emergency room, and hospitalizations. Data recorded on the diary will be collected from the patient verbally by the DCRI Call Center during the planned follow-up interviews

7.2.2 Secondary Endpoints Compared at 6 Weeks Postoperative for Non-inferiority

Standard clinical follow-up for TKR patients occurs approximately 6 weeks after surgery. At this routine visit, patients will be administered standard clinical assessments for gait speed and range of motion (ROM) in the operated knee. The DCRI call center also captures patient-reported outcome measured 6 weeks after surgery.

Non-inferiority effectiveness endpoints:

1. Survey regarding health [Knee Injury and Osteoarthritis Outcome Score (KOOS)] for pain, symptoms, activities of daily living, function in sports and recreation, and knee-related quality of life (QOL)
2. Knee ROM [lower (extension) and upper range of motion (flexion)]
3. Gait Speed

7.2.3 Secondary Endpoints Compared at 12 Weeks Postoperative for Non-inferiority

At approximately 12 weeks after surgery, the patient will be contacted again by the DCRI Call Center to collect the following data via telephone interview:

Non-inferiority effectiveness endpoints:

1. Survey regarding health (KOOS)

Non-inferiority safety endpoints:

1. Pain score
2. Any fall reported between hospital discharge and 12-week follow-up (yes/no)
3. Re-hospitalizations since hospital discharge (total count)

7.3 Additional Secondary Endpoints

Additional secondary endpoints are collected at 6 and/or 12 weeks post-operatively that are not part of non-inferiority testing for effectiveness or safety. Superiority testing will be completed for all non-inferiority endpoints and these additional secondary endpoints below.

Endpoints collected and compared at 6 weeks:

1. KOOS subdomain scores
2. Physical activity (duration of moderate exercise in total minutes per week)
3. Return to work by 6 weeks (yes, modified schedule, or no)

Endpoints collected and compared at 12 weeks:

1. KOOS subdomain scores
2. Patient-Reported Outcomes Measurement Information System (PROMIS) – Physical Health (PH)
3. Patient-Reported Outcomes Measurement Information System (PROMIS) – Mental Health (MH)
4. Satisfaction with Physical Function (questionnaire)
5. Physical activity (duration of moderate exercise in total minutes per week)
6. Return to work by 12 weeks (yes/modified schedule/no)
7. Satisfaction with tele-rehab platform (*intervention patients only thus just tabulated*)

Endpoints collected at both 6 weeks and 12 weeks post-operatively but compared only at 12 weeks (*patient diary and interview data that need to be combined to represent the entire 12 weeks*):

1. Adherence to prescribed PT regimen (# days per week, adherence [5 categories], and reasons for not done as prescribed)
2. Healthcare encounters – 8 types (total PT visits, calls/emails to PT, MD office visits, MD phone calls/emails, re-hospitalizations, urgent care or ER visit, inpatient re-habilitation stay, and skilled nursing facility stay)
3. Progress toward personal recovery goal [actual score, score=10 (yes/no), and time to meeting goal]

7.4 Exploratory Endpoints

Exploratory endpoints will include effectiveness endpoints evaluated for superiority, as well as comparison of change over time for endpoints assessed at multiple time points both within and between treatment groups.

Effectiveness and safety endpoints evaluated for superiority:

1. ROM (upper and lower) at 6 weeks
2. Gait speed (6 weeks)
3. Pain score (6 and 12 weeks)
4. KOOS overall score (6 and 12 weeks)

Effectiveness and safety endpoints evaluated for change over time:

1. Change in KOOS (baseline-6 weeks, 6-12 weeks and baseline-12 weeks)
2. Change in gait speed (hospital discharge to 6 weeks)
3. Change in pain score over time (discharge to 6 weeks, 6-12 weeks, and discharge to 12 weeks)

Other secondary endpoints evaluated for change from baseline to 12 weeks:

1. Progress toward recovery goal
2. PROMIS Global and Mental Health
3. Satisfaction with Physical Function
4. Physical activity

7.5 Randomization

It is anticipated that a total of 306 subjects will be randomized to one of the two treatment groups. Once a subject has provided informed consent and eligibility criteria have been confirmed, the site-designee will access the secure, study website to randomize the subject and receive the subject's assignment number. While the subjects, Investigator, and Sponsor are not blinded to treatment assignment due to study implementation requirements, aggregated data will remain blinded to all until the database is locked.

Subjects will be randomized by site in a 1:1 ratio to receive either tele-rehab-supported PT or traditional home and/or clinic-based PT. In either case, randomization must occur no less than 10 days prior to the patient's surgery date, or the patient will be considered ineligible.

8 DATA SOURCES

8.1 DCRI Registry System

Enrollment and randomization of subjects will be handled by a secure, password protected web-based electronic data collection tool (DCRI Registry System) for site coordinators to abstract medical record information about each patient after informed consent is obtained. Collection time points include randomization, baseline (enrollment visit), hospital discharge, and 6 weeks after discharge.

8.2 DCRI Call Center

DCRI Call Center staff will contact all patients via telephone approximately 6 and 12 weeks after hospital discharge to administer the follow-up surveys/assessments and collect details from the patient diary.

8.3 Adverse Events

Reporting of any adverse events discovered during the course of the study will be the responsibility of care providers at the local site and should be made using the appropriate mechanism (e.g., FDA Medwatch).

8.4 Final Study Report

The final study report will be based on data collected either through the DCRI Registry System (CRF data) or DCRI Call Center (survey/questionnaire and patient diary data).

9 GENERAL METHODOLOGY

Descriptive statistics will be grouped into three categories: Tele-rehab PT, Traditional PT, and Overall. Continuous variables will be summarized by the number of observations and the mean, standard deviation, median, minimum, and maximum values. For categorical data, the counts, denominators and percent per category will be presented within non-missing observations. Subjects with a missing value for a variable will not be included in the calculation for that variable. All continuous data will be summarized with one more significant digit than in the dataset. Percentages will be rounded to one digit to the right of the decimal. Subjects with missing categorical data will not be included in calculations of percentages for that variable unless otherwise specified. No imputation will be made for missing values. Both the frequency and the associated denominator will be shown to facilitate review of missing categorical data. Categorical responses of "Unknown" will be set to missing.

It is anticipated that both the 6- and 12-week follow-up calls will not occur exactly at 6 and 12 weeks post-op, respectively, for every patient. However, the DCRI Call Center is instructed to contact subjects as close as possible to the appropriate time since postoperative discharge date. Data needed for the primary endpoint will be prioritized if patients agree to spend only a limited time on the follow-up call.

All statistical tests will be one-sided (non-inferiority) or two-sided (superiority) with a significance level of 0.05, unless otherwise documented. Tests for differences between treatment groups for endpoints that are not protocol-specified may be performed. Unless otherwise stated, continuous variables will be compared between groups with two-sample student t-test or with Wilcoxon's rank-sum test depending on normality assumptions.

When it is necessary to detect differences between groups, unless it is stated otherwise, categorical values will be compared using the chi-square test or Fisher's exact test. The chi-square test will be used when all cells in the table of the categorical comparison have an expected value of 5 or above. Otherwise, a Fisher's exact test will be performed.

All tables will be presented with summary statistics overall and by treatment group unless otherwise specified.

All analyses will be completed using SAS version 9.4 or higher.

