- Healthcare encounters since hospital discharge, and weekly status of personal recovery goal (patient diary entries)

4.5 12 Weeks Post-Op

At approximately 12 weeks after surgery, the patient will be contacted again by the DCRI Call Center to collect the following data via telephone interview. The interview is expected to last approximately 20 minutes:

- Surveys regarding health (KOOS, PROMIS, Satisfaction with Physical Function)
- Adherence to prescribed PT regimen
- Physical activity
- Falls since last interview
- Healthcare encounters since last interview, and weekly status of personal recovery goal (patient diary entries)
- Thoughts about the tele-rehab platform (intervention patients only)

Also at 12 weeks after surgery, select sites may be asked to provide a summary of enrolled patients' outpatient clinic encounters (phone, email, in person) with orthopedic staff and physical therapists. This may be used to validate patient-reported encounters from the diary. Collection of the information, if requested, may be facilitated using the medical record release form signed by the patient at the time of enrollment.

5. Statistical Methods

The goal of this study is to assess the cost of the episode of care for total knee replacement, and whether the use of a tele-rehab platform is successful in mitigating some of those costs. The episode for analysis will be from surgery through 3 months post-discharge, in alignment with the new Comprehensive Care for Joint Replacement (CJR) bundled payment model being piloted by the Centers for Medicare and Medicaid Services (CMS). This will be a time-driven activity-based cost (TDABC) analysis. DCRI will be responsible for regular reporting of enrollment statistics, data quality, and data query status to the sponsor.

In addition to assessing the primary objective of cost, the study also will assess standard clinical measures of recovery (range of motion, gait speed) and qualitative measures of patient perceptions regarding their health and functional status (patient surveys) using both standardized and non-standardized tools. These assessments are intended to demonstrate the non-inferiority hypothesis that patients receiving PT via the tele-rehab platform did not have worse outcomes than patients receiving traditional in-person PT.

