5.1. Sample Size

The primary aim of this study is to assess the difference in outpatient post-surgical costs between the control and intervention groups. The exact post-procedure cost estimates under study are unknown; however, we can estimate that an effect size of approximately 0.33 can be detected with 150 subjects per group with at least 80% power. The effect size is the ratio of the mean difference over the standard deviation (SD) assumed for each population, while the coefficient of variation (CV) is the ratio of the population mean over the SD. Lower variability would enable detection of a smaller cost difference, or the detection of a larger difference with fewer patients. The below table gives several mean ratios that could be detected with 80% power and 300 subjects where R1 is the ratio of the means (Control / Intervention) at which the power is calculated using a two-sample t-test with equal variance and a significance level of 0.05.

Power	N1	N2	N	R0	R1	Effect		
						Size	CV	Alpha
0.8023	150	150	300	1.000	1.033	0.3255	0.1	0.050
0.8070	150	150	300	1.000	1.067	0.3275	0.2	0.050
0.8003	150	150	300	1.000	1.100	0.3247	0.3	0.050
0.8045	150	150	300	1.000	1.134	0.3264	0.4	0.050
0.8184	150	150	300	1.000	1.170	0.3324	0.5	0.050
0.8101	150	150	300	1.000	1.200	0.3288	0.6	0.050
0.8078	150	150	300	1.000	1.230	0.3278	0.7	0.050
0.8096	150	150	300	1.000	1.260	0.3286	0.8	0.050
0.8143	150	150	300	1.000	1.290	0.3306	0.9	0.050
0.8209	150	150	300	1.000	1.320	0.3335	1.0	0.050
0.8098	150	150	300	1.000	1.340	0.3287	1.1	0.050
0.8025	150	150	300	1.000	1.360	0.3256	1.2	0.050
0.8153	150	150	300	1.000	1.390	0.3310	1.3	0.050
0.8125	150	150	300	1.000	1.410	0.3298	1.4	0.050
0.8116	150	150	300	1.000	1.430	0.3295	1.5	0.050
0.8123	150	150	300	1.000	1.450	0.3297	1.6	0.050
0.8004	150	150	300	1.000	1.460	0.3247	1.7	0.050
0.8039	150	150	300	1.000	1.480	0.3262	1.8	0.050
0.8082	150	150	300	1.000	1.500	0.3280	1.9	0.050
0.8007	150	150	300	1.000	1.510	0.3248	2.0	0.050

Thus, with 300 subjects we can detect an effect size of 0.33 which represents a whole scenario of cost differences that can be detected with at least 80% power that is dependent on the variability of the costs under study. The below table illustrates some example cost differences that could be detected based on the assumed SD of the costs.

Standard Deviation (SD)	Mean Cost Difference (\$)	Standard Deviation (SD)	Mean Cost Difference (\$)
100	32.50	800	259.60
200	64.90	900	292.10
300	97.40	1000	324.50

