9.4 Accounting for Missing Data

Missing data will not be imputed. We will analyze only available information.

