9.8 Follow-up Data Collection Forms

9.8.1 6-Week Data Collection

Standard clinical follow-up for TKR patients occurs approximately 6 weeks after surgery. At this routine visit, patients will be administered standard clinical assessments for gait speed and range of motion (ROM) in the operated knee. Six-week data captured will

include the time from surgery until the date of the 6-week visit in days. Ten-meter gait speed and range of motion (ROM) upper and lower scores will be tabulated overall and by treatment group. Comparisons between treatment groups will be based on an analysis as described Sections 9.11 and 9.12.

9.8.2 6-Week Patient Survey

The DCRI call center captures patient-reported outcome measured 6 weeks after surgery, including fallen since hospital discharge (yes/no), pain score, physical activity (frequency and duration of exercise) and return to work (yes/no, and if yes, same or modified schedule). These 6-week variables will be summarized overall and by treatment group.

The KOOS Knee Survey Questionnaire will also be administered at 6-weeks. Responses will be tabulated overall and by treatment group for each question response as well as for the total score; however, no statistical comparisons will be done on the individual responses. The KOOS junior can be used at the 6-week visit. The overall KOOS score will be evaluated for both superiority and non-inferiority at 6-weeks, while the KOOS subdomain scores will only be compared for superiority as part of the exploratory analyses.

9.8.3 3-Month Patient Survey

At this visit, patients will be again be contacted by the DCRI call center to capture patient-reported outcomes, including fallen since last interview (yes/no), pain score, total re-hospitalizations since discharge, physical activity (frequency and duration of exercise) and return to work (yes/no, and if yes, same or modified schedule).

Additional survey data collected will include the Satisfaction with Physical Function Survey, the PROMIS Global Health Survey, the PROMIS Global Mental Survey, and the KOOS Knee Survey Questionnaire. Responses will be tabulated overall and by treatment group for each question response; however, no statistical comparisons will be done for the individual responses. The overall KOOS score and individual subscale scores will be compared. The KOOS junior cannot be used at the 3 month time point for efficacy analysis but can be used to evaluate change from 6 weeks to 3 months.

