9.9 Power and Sample Size Calculations

The primary aim of this study is to assess the difference in outpatient post-surgical costs between the control and intervention groups at 12-weeks post-operative. The exact post-procedure cost estimates under study are unknown; however, we can estimate that an effect size of approximately 0.33 can be detected with 150 subjects per group with at least 80% power. The effect size is the ratio of the mean difference over the standard deviation (SD) assumed for each population. Lower variability would enable detection of a smaller cost difference, or the detection of a larger difference with fewer patients. The sample size estimates were made assuming a two-sample t-test with equal variance and a significance level of 0.05. Thus, with 300 subjects we can detect an effect size of 0.33 which represents a whole scenario of cost differences that can be detected with at least 80% power that is dependent on the variability of the costs under study. The below table illustrates some example cost differences that could be detected based on the assumed SD of the costs.

Standard Deviation (SD)	Mean Cost Difference (\$)	Standard Deviation (SD)	Mean Cost Difference (\$)
100	32.50	800	259.60
200	64.90	900	292.10
300	97.40	1000	324.50
400	129.80	1100	357.00
500	162.30	1200	389.50
600	194.70	1300	421.90
700	227.20	1400	454.40
750	243.40	1500	486.80

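### The limited-call rule in SAP 9 protects only cost data, so the one-question falls and pain safety endpoints are at risk of being lost

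*SAP*

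**What the plan says.** SAP section 9 expects that some patients will accept only a short call, and gives one rule for it: "Data needed for the primary endpoint will be prioritized if patients agree to spend only a limited time on the follow-up call". SAP 7.2.1 and 9.10 define the primary endpoint as 12-week health service cost, built from the healthcare encounters in the patient diary.

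SAP 9.11.2 rests the safety hypothesis on three 12-week endpoints: pain (margin 1.7), re-hospitalizations (margin 1) and any fall since discharge (margin 10%, read here as percentage points). All three must pass. Re-hospitalizations enter the cost formula, so the rule covers them. Pain and falls do not.

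On missing values, SAP 9.4 says: "Missing data will not be imputed. We will analyze only available information".

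Both unprotected items are short. Falls is a yes/no answer at each call (SAP 9.11.2), and pain is a single 0-10 scale (Protocol 3.5). The 12-week call list in Protocol 4.5 has no separate pain item. Footnote 6 to Table 1 in both documents takes the PROMIS pain scale alone when the full PROMIS is not given, and SAP Table 1 applies that footnote at 6 and 12 weeks. Of the whole 12-week call, Protocol 4.5 says: "The interview is expected to last approximately 20 minutes".

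KOOS, the 12-week effectiveness endpoint, is also outside the rule. Its short form does not help there, because SAP 9.8.3 says: "The KOOS junior cannot be used at the 3 month time point for efficacy analysis".

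**The concern.** The rule names one protected category and is silent on everything else. Two of the three endpoints that decide the safety claim fall into that silence, although each needs only one question. Patients who shorten a call may be less well than those who finish it. If so, an available-case analysis would understate falls and pain. In a non-inferiority comparison, understating harm in the intervention arm favours the claim, and an answer not collected on the call may not be recoverable later. The stake is whether the safety hypothesis is tested on nearly all operated patients or on those willing to talk for longer.

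**Working it through.** **The plan's own figure.** SAP 9.9 states that "an effect size of approximately 0.33 can be detected with 150 subjects per group with at least 80% power". Protocol 5.1 says that "the power is calculated using a two-sample t-test with equal variance and a significance level of 0.05". For the first row of its table (effect size 0.3255, 150 per arm), the noncentrality is 0.3255 × √(150/2) = 2.819 with 298 degrees of freedom. The noncentral t gives power 0.8023, as stated. This figure concerns cost only. The documents give no power for falls or pain, no expected fall rate and no expected missing rate, so those are assumptions below.

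**Inputs.** From the documents: 150 per arm, one-sided 0.05 for non-inferiority (SAP 9), falls margin 0.10, pain margin 1.7. Assumed: fall rate 10-20% for power and 10-30% for bias, pain SD 2-3, missing 0-30%. A patient without a falls answer is taken to leave the falls analysis. I found no SAP rule for a no at 6 weeks followed by a missing 12-week answer.

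**Step 1: falls power with equal true rates p.** Power = Φ(0.10/SE − 1.645), with SE = √(2p(1−p)/n). For p = 0.15:

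- n = 150: SE = 0.0412, power Φ(0.78) = 0.78
- n = 135 (10% missing): SE = 0.0435, power Φ(0.66) = 0.74
- n = 120 (20% missing): SE = 0.0461, power Φ(0.52) = 0.70

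The same sequence (0%, 10%, 20% missing) is 0.89, 0.86, 0.83 at p = 0.10 and 0.70, 0.66, 0.62 at p = 0.20.

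**Step 2: unequal loss unrelated to falling.** Take true falls of 20% (intervention) versus 10% (control), exactly at the margin, with 20% versus 10% missing at random. The expected difference stays at 10 points, so the chance of falsely showing non-inferiority is Φ(−1.645) = 0.05. Unequal rates alone do not bias the test.

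**Step 3: loss related to falling, in one arm.** Observed rate = p(1−mf) / [p(1−mf) + (1−p)(1−mn)], where mf and mn are the missing proportions in fallers and non-fallers. Keep 20% versus 10%, with 10% missing everywhere except among intervention-arm fallers. The false non-inferiority rate is Φ((0.10 − observed difference)/SE − 1.645).

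- mf = 20%: observed 0.16/0.88 = 18.2%, difference 8.2 points, false rate 0.11
- mf = 30%: observed 0.14/0.86 = 16.3%, difference 6.3 points, false rate 0.23
- mf = 40%: observed 0.12/0.84 = 14.3%, difference 4.3 points, false rate 0.41

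Overall missingness in the intervention arm is then only 12%, 14% or 16%, against 10% in control. With true falls of 30% versus 20%, the false rates are 0.12, 0.25 and 0.45.

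**Step 4: the same falls-related loss in both arms.** If the true rates are equal, the distortion cancels. At the margin (20% versus 10%) it cancels only in part. With fallers missing at 20% in both arms, the difference is 9.2 points and the false rate 0.07. At 40% in both arms they are 7.4 points and 0.17.

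**Step 5: pain.** Power = Φ(1.7/(SD√(2/n)) − 1.645). In the worst case examined, SD 3 with 30% missing (n = 105), SE = 0.414 and power is Φ(2.46) = 0.99. If 20% of one arm is missing and those patients average 2 points worse than the patients observed, the arm mean shifts by 0.20 × 2 = 0.4, against a margin of 1.7.

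**The case against.** Protecting the primary endpoint on a short call is a legitimate choice, and the SAP never says that other items are skipped. It sets a priority and leaves the order of the rest to the call script (Protocol 3.6.3), which is intended to limit missing variables. The lists in Protocol 4.4 and 4.5 place falls just before the healthcare encounters. A stand-alone pain item already exists under footnote 6. The Call Center works days, nights and weekends and has a toll-free line for completing interviews. SAP 9 shows denominators for categorical data, and Protocol 5.3 promises to look into reasons for missing data.

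Most of this stands, and it means that the loss is a risk and not a documented outcome. It does not close the gap. Footnote 6 supplies a pain item but does not rank it on a limited call, the listed order is not a rule, and showing denominators does not recover lost answers.

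A reader might infer three stronger points that the documents do not support:

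- **That the arms will differ because control patients have more PT visits to list.** Both arms keep the same diary, PT visits are compared in both arms (SAP 7.3), and intervention patients may also receive in-person PT (Protocol 3.4.1). The only arm-specific call content documented is the tele-rehab module, in the intervention arm.
- **That asking about PT first unblinds the interviewer.** The trial is open label (SAP 7.5), that module already reveals the arm, and no passage claims blinded interviewers.
- **That unequal short-call rates by themselves bias the comparison.** Step 2 shows that they do not.

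**Conclusion.** The point holds as a gap that is cheap to close. The limited-call rule leaves falls and pain unprotected, both are needed for the safety claim, and nothing is imputed. The size of the loss, and any difference by arm, cannot be known from the documents.

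Falls is the materially exposed endpoint. Random loss of 10-20% costs about 4 to 8 points of power at a 15% fall rate, where power is already only 0.78 with no loss, so call order is not the main limit on that test. The more serious case is falls-related loss concentrated in the intervention arm, where false non-inferiority could reach 0.11-0.41 while overall missingness looks unremarkable. That range depends on the assumed 20% versus 10% fall rates and on 20-40% of intervention-arm fallers being missing. Pain has ample room under the assumed SDs of 2 to 3. It belongs in the protected set because it costs one question, not because its test is fragile.

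**What to change.** Change the sentence in SAP 9, and the call script to match, so that the protected minimum for a limited call is:

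1. the falls item (yes/no) and the stand-alone pain item (footnote 6), together with the healthcare encounters needed for cost;
2. KOOS next;
3. a call-back through the existing Call Center if KOOS is not reached.

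Two optional additions take no call time: state how a no at 6 weeks with a missing 12-week falls answer is counted, and report limited calls and item missingness by arm.

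The cost is one SAP sentence, a script revision, and some call-backs within existing Call Center hours. The downside is that a small part of a shortened call goes to two brief questions. No new data item is needed.
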